4.2. Discussion of Study Design, Including the Choice of Control Groups

This study is designed to obtain preliminary estimates of the safety and immune response induced by the BPZE1 lyophilized vaccine. Fifteen placebo recipients are included in order to partially blind the subjects and observer.

4.3. Selection of Study Population

The study population for DMID protocol 17-0010 is males and non-pregnant females, 18 to 49 years old, inclusive, who are in good health and meet all eligibility criteria. Potential subjects will be screened from the general population at VUMC by history, physical exam, clinical laboratory tests including White Blood Cells (WBC), Hemoglobin (Hgb), platelets, serum IgG antibodies, alanine aminotransferase (ALT), Creatinine, and Human Immunodeficiency Virus (HIV), and a urine or serum pregnancy test. Potential subjects with close contact, defined as sharing a household, serving as a healthcare worker, or working professionally in settings with repeated exposures, with children less than 1 year of age or with persons with known immunocompromising conditions will be excluded. Otherwise eligible potential subjects experiencing an acute illness, including temperature $>100^{\circ}\text{F}$, will be eligible for postponed enrollment within the screening window or rescreening once symptoms resolve.

4.4. Treatments

4.4.1. Treatments Administered

Subjects are administered one dose (either 10^7 CFU or 10^9 CFU) of lyophilized, live-attenuated *Bordetella pertussis* vaccine (BPZE1) or placebo.

4.4.2. Identity of Investigational Product(s)

The investigational BPZE1 lyophilized vaccine is for nasal administration and contains [REDACTED]. The placebo consists of the same constituents in the same quantities as the BPZE1 investigational vaccines, absent the [REDACTED]. Both were provided by [REDACTED].

4.4.3. Method of Assigning Subjects to Treatment Groups (Randomization)

Enrollment/randomization will be performed through the enrollment module in the electronic data capture system, maintained by the SDCC. Eligible subjects will be randomized and assigned in a 3:3:3:1 ratio to BPZE1 10^7 CFU administered via VaxINator: BPZE1 10^9 CFU administered via VaxINator: placebo

administered via VaxINator: BPZE1 10^9 CFU administered via Needleless Tuberculin Syringe. The randomization is based on a block scheme to provide an approximately balanced allocation to the treatment groups during the study.

4.4.4. Selection of Doses in the Study

In a Phase 1a clinical study, a dose of 10^7 CFU of the liquid formulation of BPZE1 administered nasally resulted in colonization of the mucosal surface in 42% of subjects with no serious adverse events. [12] In a Phase 1b clinical study, also using the liquid formulation administered nasally, but in a greater volume (400 μ L per nostril), doses of 10^7 , 10^8 , and 10^9 CFU all resulted in colonization in $\geq 75\%$ of subjects with faster colonization rate and faster clearance rate being correlated with higher dosage. [13] No serious adverse events were observed in any of the dosage groups and there were no detectable differences in adverse events between dosage groups. The lyophilized formulation is hypothesized to share similar safety characteristics with the liquid formulation.

4.4.5. Selection and Timing of Dose for Each Subject

Subjects are assigned randomly to treatment groups in a 3:3:3:1 ratio (BPZE1 10^7 CFU administered via VaxINator: BPZE1 10^9 CFU administered via VaxINator: placebo administered via VaxINator: BPZE1 10^9 CFU administered via needleless tuberculin syringe). Each subject will receive a single intranasal dose in clinic on Day 1. Timing of dose is not specified.

4.4.6. Blinding

This is a partially-blind clinical trial as the method of immunization (i.e. VaxINator vs. needleless syringe) will be known. After reconstitution and transfer to a 1-mL syringe, the 10^7 CFU dose investigational vaccine and the placebo are transparent and indistinguishable while the 10^9 CFU dose can be discriminated from the placebo and the 10^7 CFU dose due to its opaque appearance. Therefore, syringes will be wrapped with a colored sleeve to avoid potential unblinding of study personnel or the subject. Investigators, the subject, and study personnel will remain blinded to allocation of BPZE1 or placebo.

The randomization scheme will be generated by the SDCC and provided to unblinded study personnel (i.e., research pharmacists performing study vaccination preparations and unblinded study vaccine administrators) at the participating VTEU site.

The unblinded study vaccine administrator is a study personnel member credentialed to administer vaccines and may also participate in dose preparation but will not be involved in study-related assessments or have subject contact for data collection following study vaccine administration. Laboratory personnel performing immunogenicity assays will be blinded to study assignment.

Upon request by the participating VTEU site, and at the discretion of DMID, unmasking may occur after all data have been locked at Day 181, analyzed, interpreted, and the final CSR has been completed. The Safety Monitoring Committee (SMC) may receive data in aggregate and presented by treatment arm. The SMC may also be provided with expected and observed rates of the expected AEs in an unblinded fashion and may request the treatment arm be unblinded for an individual subject if required for safety assessment. The SMC will review grouped and unblinded data in the closed session only.

4.4.7. Prior and Concomitant Therapy

Administration of medications, therapies, or vaccines will be recorded on the appropriate data collection form. Concomitant medications will include all current medications and medications taken within 30 days prior to

signing the informed consent form through approximately 28 days after study vaccination (or through the early termination visit if prior to that time). Prescription and over-the-counter drugs will be included, as well as herbals, vitamins and supplements. In addition, receipt of non-study vaccines will be solicited through approximately 181 days after study vaccination and reported in the eCRF.

4.4.8. Treatment Compliance

Subject compliance is not expected to be an issue because all subjects are to receive a single dose of study product administered in the clinic by a study personnel member who is unblinded to subject treatment assignment.

4.5. Efficacy (Immunogenicity) and Safety Variables

See [Table 1](#) and [Table 2](#) for a schedule of study procedures.

4.5.1. Safety Variables

Safety will be assessed by the frequency and severity of:

1. Serious adverse events (SAE) occurring from the time of vaccination through approximately 6 months after vaccination.
2. Solicited Adverse Events – reactogenicity events occurring from the time of each study vaccination through 14 days after study vaccination:
 - a. Mucosal reactions including runny nose, stuffy nose/congestion, nasal pain/irritation, epistaxis, sneezing, sinus pressure/pain, sore throat, cough, and shortness of breath, cough, rhinorrhea, and sneezing
 - b. Systemic reactions including fever, chills, fatigue, malaise, myalgia, arthralgia, headache, and hypersensitivity.
3. Unsolicited Adverse Events – study vaccine-related non-serious adverse events occurring from the time of study vaccination through approximately 28 days after study vaccination.
4. New onset chronic medical conditions (NOCMCs) and adverse events of special interest (AESI) – NOCMC's will be assessed throughout the follow-up period, while medically attended wheezing events (an AESI) will be collected through Day 29 post-vaccination.

4.5.2. Immunogenicity Variables

Humoral immune response will be assessed from venous blood samples collected at screening and on Days 1, 15, 29, and 181

Mucosal immune response will be determined by ELISA on specimens collected by nasal wick at screening for baseline immunology and again on Day 29 and Day 181.

Immunogenicity will be assessed by the Vanderbilt Vaccine Research Program Laboratory.

4.5.3. Nasal Clearance Variables

Nasal clearance of *B. pertussis* will be determined by culture on specimens collected by nasal swab. The nasopharyngeal culture result will be reported as a binary outcome (i.e. bacteria detected / no bacteria detected) at Day 29 and Day 46 for subjects who remained positive at Day 29.

5. SAMPLE SIZE CONSIDERATIONS

This study is planned to enroll approximately 50 healthy adults randomized into four treatment groups in a 3:3:3:1 ratio, as described in [Section 4.4.3](#). [Table 3](#) and [Table 4](#) in the appendices describe the probability of observing safety events and the minimum detectable difference in seroconversion rates for the planned sample size.

[Table 3](#) indicates the probability of observing one or more safety events (such as solicited local or systemic reactogenicity events, or an unsolicited non-serious AE of a particular type) for a treatment arm with the assumed event frequency and for the given sample size. For example, for any of the treatment arms with a sample size of 15 subjects, there is a 79.4% probability of detecting an AE that occurs at a frequency of 10%, and a 14% probability if the AE occurs at a rate of 1%.

One of the secondary outcome measures is the proportion of subjects that achieve seroconversion to individual pertussis antigens (PT, FHA, PRN, and FIM 2/3) by serum IgG or IgA ELISA at Days 15, 29 and 181 for humoral immune response. [Table 4](#) shows the minimum detectable differences with 80% power between the proportion of subjects attaining seroconversion in the BPZE1 by VaxINator group versus Placebo using a two-sided Fisher's Exact test and $\alpha = 0.05$.

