11.2 Sample Size Considerations

The study population for this clinical trial includes healthy male and non-pregnant female subjects 18-49 years of age, inclusive, who meet all eligibility criteria. Study subjects will be recruited from the general population at the Vanderbilt University Medical Center VTEU site. This study is planned to enroll approximately 50 healthy adults randomized into four treatment groups in a 3:3:3:1 ratio, as described in [Table 2 \(Section 4\)](#). The tables below describe the probability of observing safety events and the minimum detectable difference in seroconversion rates for the planned sample size.

[Table 3](#) indicates the probability of observing one or more safety events (such as solicited local or systemic reactogenicity events, or an unsolicited non-serious AE of a particular type) for a treatment arm with the assumed event frequency and for the given sample size. For example, for any of the treatment arms with a sample size of 15 subjects, there is a 79.4% probability of detecting an AE that occurs at a frequency of 10%, and a 14% probability if the AE occurs at a rate of 1%.

Table 3: Probability (%) of Observing at Least One Adverse Event

| Event Frequency | N = 5 | N=15 |
|------------------------|--------------|-------------|
| ≥0.01% Rare | <0.1 | <0.1 |
| ≥0.1% Uncommon | 0.5 | 1.5 |
| ≥1% Common | 4.9 | 14.0 |
| ≥10% Very Common | 41.0 | 79.4 |

One of the secondary outcome measures is the proportion of subjects that achieve seroconversion to individual pertussis antigens (PT, FHA, PRN, and FIM 2/3) by serum IgG or IgA ELISA at Days 15, 29 and 181 for humoral immune response. Table 4 shows the minimum detectable differences with 80% power between the proportion of subjects attaining seroconversion in the BPZE1 by VaxINator group versus Placebo using a two-sided Fisher’s Exact test and alpha = 0.05.

Table 4: Minimum Detectable Difference in Proportion of Subjects Attaining Seroconversion comparing Placebo versus the BPZE1 (107 or 109 CFU)

| Placebo by VaxINator | BPZE1 (10 ⁷ or 10 ⁹ CFU) by VaxINator | Assumed Proportion of Subjects Attaining Seroconversion (Placebo) | Proportion of Subjects Attaining Seroconversion (BPZE1) | Minimum Detectable Difference (Treatment – Placebo) |
|----------------------|---|---|---|---|
| N=15 | N=15 | 0.00 | 0.41 | 0.41 |
| | | 0.01 | 0.43 | 0.42 |
| | | 0.05 | 0.54 | 0.49 |
| | | 0.10 | 0.63 | 0.53 |
| | | 0.20 | 0.76 | 0.56 |

N=Sample Size

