8.1. Secondary Immunogenicity Analysis

Summaries and analysis of immunogenicity data will be presented for the immunogenicity and PP populations by treatment group.

Immune responses in terms of toxin-specific serum IgG and IgA antibody titers (PT, FHA, PRN, FIM 2/3) will be summarized at each time point. Analyses will include the Geometric Mean Titers (GMTs) along with corresponding 95% confidence intervals (Table 17, Table 18, Table 19, and Table 20) and Geometric Mean Fold Rise (GMFR) (Table 21, Table 22, Table 23, and Table 24), as well as the proportion of subjects achieving seroconversion (defined as 2-fold increase over baseline of GMT) for each antigen (PT, FHA, PRN, and FIM 2/3) and the proportion of subjects that achieved seroconversion for ≥ 1 (Table 25 and Table 26) and ≥ 2 (Table 27 and Table 28) antigens (PT, FHA, PRN, and FIM 2/3.) Rates of seroconversion will be compared using Barnard's exact test. Reverse cumulative distributions (RCD) curves will also be presented for PT, FHA, PRN, and FIM 2/3 antibody titers. Plots for each assay will be generated with four panels (pre-vaccination, Day 15, Day 29, and Day 181), and separate curves within each panel for each treatment group, as shown in Figure 3, Figure 4, Figure 5, and Figure 6. Individual immunogenicity response data will also be presented (Listing 7 and Listing 8.)

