Immune responses in terms of the ratio of toxin-specific (PT, FHA, PRN, FIM 2/3) nasal mucosal IgA antibody to total nasal mucosal IgA antibody will be summarized at each time point (Table 29 and Table 30.) Analyses will include the geometric mean titer ratios (GMTR) of antigen-specific IgA to total IgA and corresponding 95% confidence intervals, along with fold change of the GMTR from baseline. The proportion of subjects achieving seroconversion, defined as ≥ 2 -fold rise of the GMTR from baseline, to each antigen (PT, FHA, PRN, and FIM 2/3) will be reported (Table 29 and Table 30) as well as the proportion of subjects that achieve seroconversion by nasal aspirate ELISA to one or more (Table 31 and Table 32) antigens (PT, FHA, PRN, and FIM 2/3) at either or both of Day 29 and Day 181. Rates of seroconversion will be compared using Barnard's exact test. Reverse cumulative distributions (RCD) curves will also be presented for mucosal PT, FHA, PRN, and FIM 2/3 antibody titers. Plots for each assay will be generated with three panels (pre-vaccination, Day 15, Day 29, and Day 181), and separate curves within each panel for each treatment group, as shown in Figure 7 and Figure 8. Individual immunogenicity response data will also be presented (Listing 9.)

Subjects will be tested for *B. pertussis* colonization by culture at Day 29 and, if positive, again at Day 46. The proportion of subjects with positive *B. pertussis* culture will be reported for the PP population at each time point with corresponding 95% confidence intervals (Table 33.) Individual nasal colonization data will also be presented (Listing 13.)

No formal hypothesis testing is planned.

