9.7.1 Sample Size

Table 3: Probability (%) of Observing at Least One Adverse Event*

Event Frequency	N = 5	N=15
≥0.01% Rare	<0.1	<0.1
≥0.1% Uncommon	0.5	1.5
≥1% Common	4.9	14.0
≥10% Very Common	41.0	79.4

Table 4: Minimum Detectable Difference in Proportion of Subjects Attaining Seroconversion comparing Placebo versus the BPZE1 (10⁷ or 10⁹ CFU)*

Placebo by VaxINator	BPZE1 (10⁷ or 10⁹ CFU) by VaxINator	Assumed Proportion of Subjects Attaining Seroconversion (Placebo)	Proportion of Subjects Attaining Seroconversion (BPZE1)	Minimum Detectable Difference (Treatment – Placebo)
N=15	N=15	0.00	0.41	0.41
		0.01	0.43	0.42
		0.05	0.54	0.49
		0.10	0.63	0.53
		0.20	0.76	0.56

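### SAP Table 4 gives detectable differences for Fisher's exact test, but seroconversion will be compared with Barnard's test, so the stated 80% power understates that of the planned comparison; one Table 3 cell is also wrong.

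*SAP*

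**What the plan says.** SAP section 5 says that Table 4 "shows the minimum detectable differences with 80% power between the proportion of subjects attaining seroconversion in the BPZE1 by VaxINator group versus Placebo". The same sentence goes on to name the test: "versus Placebo using a two-sided Fisher's Exact test". Protocol section 11.2 carries the same text and the same table, with "Exact test and alpha = 0.05". Subjects are "randomized into four treatment groups in a 3:3:3:1 ratio", which gives 15 against 15 for each VaxINator dose against placebo.

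For the analysis, SAP section 8.1 says "Rates of seroconversion will be compared using Barnard's exact test", once for serum and once for mucosal responses. The footnotes to the shells for Tables 21, 25, 29 and 31 name Barnard's test again, and the remaining seroconversion tables follow the same formats. No alpha or sidedness is given for it. The SAP names Fisher's test as an analysis method only for solicited adverse events (section 9.3.1). Protocol section 11.4.3, on immunogenicity, names no test.

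Table 3, "Probability (%) of Observing at Least One Adverse Event", prints a value below 0.1 for an event frequency of 0.01% at N=15. Both documents carry that cell.

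**The concern.** A detectable difference belongs to a particular test at a particular level. At 15 per arm, Fisher's conditional test and Barnard's unconditional test have clearly different rejection regions, so a table worked for one does not describe the other. Anyone who uses Table 4 to judge what the seroconversion comparisons could have detected, for instance when a dose comparison with placebo is not significant, would be using the wrong figures. The results are meant to inform the Phase 2b dose (Protocol section 11.4), and the seroconversion tables are marked for the preliminary report, so these figures are likely to be read. Because the SAP sets no level or sidedness for Barnard's test, a reader can only borrow 0.05 from a section that describes another test.

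**Working it through.** **Inputs.** n = 15 per arm, two-sided alpha 0.05, 80% power, and the five pairs of rates, all from SAP section 5 and Table 4. Two-sided 0.05 for Barnard's test is an assumption, because the SAP gives none.

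**Method.** For each of the 16 × 16 = 256 possible outcomes (x placebo responders, y BPZE1 responders), find the p-value. Power is the sum of Bin(x; 15, p0) × Bin(y; 15, p1) over outcomes with p ≤ 0.05. Barnard's p-value is the maximum, over the common response rate, of the probability of a result at least as extreme by the pooled Wald statistic. The unpooled statistic gives the same rejection region here.

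**Row 1 by hand.** With a placebo rate of 0, x is always 0.
- Fisher, 0 against 4: p = 2 × C(15,4)/C(30,4) = 2 × 1365/27405 = 0.0996. Not rejected.
- Fisher, 0 against 5: p = 2 × C(15,5)/C(30,5) = 2 × 3003/142506 = 0.0421. Rejected.
- Fisher power at p1 = 0.41 is therefore P(Y ≥ 5) = 0.805, which reproduces the table.
- Barnard, 0 against 4: p = 0.0433. Rejected. Power at p1 = 0.41 is P(Y ≥ 4) = 0.922.
- P(Y ≥ 4) first reaches 0.80 at p1 = 0.338.

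**All rows.**

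| Placebo | BPZE1 (Table 4) | Fisher power | Barnard power | BPZE1 rate for 80% power, Barnard | Difference, Barnard | Difference, Table 4 |
|---|---|---|---|---|---|---|
| 0.00 | 0.41 | 0.805 | 0.922 | 0.338 | 0.34 | 0.41 |
| 0.01 | 0.43 | 0.792 | 0.902 | 0.365 | 0.36 | 0.42 |
| 0.05 | 0.54 | 0.805 | 0.891 | 0.471 | 0.42 | 0.49 |
| 0.10 | 0.63 | 0.793 | 0.884 | 0.571 | 0.47 | 0.53 |
| 0.20 | 0.76 | 0.805 | 0.897 | 0.697 | 0.50 | 0.56 |

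Fisher power is 0.79 to 0.81 in every row, so Table 4 is correctly calculated for the test it names.

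**Rejection boundary.** With 0, 1, 2, 3 and 4 placebo responders, significance needs 4, 6, 8, 9 and 10 BPZE1 responders under Barnard and 5, 7, 9, 10 and 11 under Fisher. The tests disagree in 20 of the 256 outcomes, and in each of these it is Barnard that rejects. The maximum true type I error is 0.018 for Fisher and 0.043 for Barnard, so both hold the 0.05 level.

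**Table 3.** P(at least one event) = 1 − (1 − 0.0001)^15 = 0.00150, or 0.15%. This is not below 0.1%. At N=5 the value is 0.05%, so the neighbouring cell is right.

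**The case against.** The strongest defence is that nothing is miscalculated and nothing is harmed. Table 4 discloses Fisher's test as its basis and is right for it. Barnard's test is valid and more powerful, so 80% is a floor. The outcomes are secondary, the sample size would not change, and section 8.1 ends with "No formal hypothesis testing is planned". All of this stands, and it limits the weight of the point. It does not make Table 4 a description of the comparisons that section 8.1 plans.

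Four stronger readings are tempting, and the documents do not support them:

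- **The trial is underpowered.** The error runs the other way.
- **The SAP departs from the protocol.** Protocol section 11.4.3 names no seroconversion test. Fisher's test appears in the protocol only for Table 4 and as an option for solicited events. Choosing Barnard's test fills a gap, so SAP section 15 has no change to record.
- **The tests will disagree on the counts this trial is going to produce.** Disagreement is confined to 20 of 256 outcomes. Phase 1b reported over 92% and 100% responders to at least one antibody at the two doses. At 92% against an assumed placebo rate of 0, 5, 10 or 20%, the chance of disagreement is 0.0, 0.01, 0.07 and 1.0%. It reaches about 9% at 0.54 against 0.05 and 16% at 0.30 against 0.05. Such rates are possible for single antigens, but the documents do not predict them.
- **The p-values contradict the absence of formal testing.** The shells give p-values only for the two BPZE1 VaxINator columns, beside differences and confidence intervals. SAP section 6.8 already says that there is no null hypothesis and no adjustment. Unadjusted descriptive p-values are compatible with that, and removing them would be a matter of taste.

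**Conclusion.** The point holds as a mismatch between the sizing test and the analysis test. If Barnard's test is run two-sided at 0.05 with 15 evaluable subjects per arm, Table 4 understates power by 8 to 12 percentage points and overstates the detectable differences by 0.06 to 0.07. The significance boundary is one BPZE1 responder lower than under Fisher for 0 to 7 placebo responders. A different level or a one-sided test would change these figures, which is why the SAP needs to state both. The Table 3 cell is a separate, small error that needs no assumption. Neither matter affects the sample size or the validity of the planned comparison; both are stated figures that should be put right.

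**What to change.** Recompute SAP Table 4 for Barnard's test: BPZE1 rates of about 0.34, 0.37, 0.47, 0.57 and 0.70 for placebo rates of 0.00, 0.01, 0.05, 0.10 and 0.20, that is, differences of about 0.34, 0.36, 0.42, 0.47 and 0.50. Name the test in section 5, and state its alpha and sidedness in sections 5 and 8.1. The alternative is to keep Table 4 and name Fisher's test, with its level and sidedness, in section 8.1 and in the footnotes of the seroconversion shells.

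In Table 3, change the cell for 0.01% and N=15 to 0.15%, or 0.1 at the table's one decimal.

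The first route costs one recalculated table, one corrected cell and a sentence in each of two sections. The second replaces the recalculated table with footnote edits. Neither changes the design, the data collected or the sample size.

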6. GENERAL STATISTICAL CONSIDERATIONS

6.1. General Principles

Unless otherwise noted, all continuous variables will be summarized using the following descriptive statistics: n (non-missing sample size), mean, standard deviation, median, maximum and minimum. The frequency and percentages (based on the non-missing sample size) of observed levels will be reported for all categorical measures. In general, all data will be listed, sorted by treatment group and subject, and when appropriate by visit number within subject. All summary tables will be structured with a column for each treatment in the order (BPZE1 10⁷ CFU administered via VaxINator, BPZE1 10⁹ CFU administered via VaxINator, BPZE1 10⁹ CFU administered via needleless tuberculin syringe, placebo administered via VaxINator) and will be annotated with the total population size relevant to that table/treatment, including any missing observations.

